5.1.1.11.2 Assessment of Time Off Ventilator

5.1.1.11.2.1 Daily Ventilator Dependence Diary

For subjects in Part 1 who have not completed the Week 24 visit and for subjects in Part 2 (including any subjects enrolled under protocol v5 and beyond), an electronic diary will be completed by the parent/LAR/caregiver to collect the type of ventilatory support and the amount of time the subject spent off of ventilatory support in a 24-hour period. The diary should be completed daily by the same parent/LAR/caregiver (whenever possible). Site staff should set up the electronic diary prior to distribution to the parent/LAR/caregiver and review the training with the parent/LAR/caregiver. The daily diary collection will begin after informed consent (or re-consent to protocol v5 or later for Part 1 subjects) and continue through Week 48. However, if after the Week 24 visit, ventilator support has been discontinued, the daily diary will no longer need to be completed. If ventilator support is resumed, the daily diary completion will resume through Week 48 or discontinuation of the ventilatory support, whichever occurs first. For

subjects in Part 1 who have already completed the Week 24 visit, a daily diary will not be completed.

5.1.1.11.2.2 Ventilator Dependence Questionnaire

A questionnaire will be completed by the parent/LAR/caregiver to collect the type of ventilatory support and the amount of time the subject spent off of ventilatory support in a 24-hour period at clinic and contact visits ([Appendix 4](#)).

For subjects in Part 1 who have already completed the Week 24 visit, the parent/LAR/caregiver will complete the ventilator dependence questionnaire at clinic and contact visits through Month 120.

For subjects in Part 1 who have not completed the Week 24 visit and for subjects in Part 2 (including any subjects enrolled under protocol v5 and beyond), the daily diary will be completed per [Section 5.1.1.11.2.1](#). After the daily diary has been stopped or the subject has completed Week 48, the parent/LAR/caregiver will complete the ventilator dependence questionnaire at clinic and contact visits through Month 120.

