5.1.1.11.4 Guidelines for Discontinuation of Ventilatory Support

Discontinuation of mechanical ventilation can be attempted after the Week 12 visit, if appropriate. The site pulmonologist and the subject's local pulmonologist, if applicable, will determine if the subject is ready to discontinue ventilatory support based on the parameters outlined in [Table 1](#) and [Table 2](#).

At the Week 12 visit, the site pulmonologist and local pulmonologist, if applicable, should review the results from the previous assessments and determine if the subject continues to meet the criteria outlined in [Table 1](#). If the subject meets the criteria in [Table 1](#), the assessments in [Table 2](#) should be conducted to assess readiness to discontinue ventilatory support. If the subject meets the criteria outlined in [Table 2](#) and the pulmonologist and Investigator determine the subject is ready, the ventilator can be discontinued. The assessments in [Table 2](#) should be conducted before discontinuing nighttime ventilation and should be repeated 3 to 4 weeks after discontinuation of nighttime ventilation. If the subject does not meet the criteria in either [Table 1](#)

and [Table 2](#), the pulmonologist should continue to assess the subject at subsequent visits to determine readiness to discontinue ventilatory support. Details on assessment for discontinuation of ventilatory support and for decannulation will be provided in a separate procedure manual.

It is advisable to wean tracheostomized subjects directly off ventilation to spontaneous respiration rather than to noninvasive ventilation (NIV) as an intermediate step because the masks required for NIV are not likely to be tolerated by infants and toddlers unaccustomed to masks.

Table 2: Required Ventilator Discontinuation Parameters

Assessments	Parameters
Gas exchange markers	
Sprinting (video record the assessment)	
 No distress SpO₂ > 94% TCO₂ ≤ 45 mmHg No intercostal retraction, tachypnea, respiratory paradox, or phase delay
Nocturnal Polysomnogram (PSG) (performed with trach open)	
Apnea-hypopnea index (AHI)	< 5 (lower threshold for NMD than for obstructive processes)
TCO ₂	35-45 mmHg
ETCO ₂	
 Consider % of sleep time with ETCO₂ < 45 mmHg and <50 mmHg Steady state capnometry in NREM and in REM sleep
Oxygen saturation (SpO ₂)	> 94%
Respiration rate (RR)	Within the age adjusted norms

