1.1.3 Estimand

The estimand of the primary objective is defined by the following 5 attributes:

- Treatment: Single dose of AT132
- Population: Male participants with ventilator-dependent XLMTM, as defined by the inclusion/exclusion criteria of the study
- Endpoint: Change from baseline in hours per day of ventilation support at Week 24
- Intercurrent events and their corresponding strategies: For study discontinuation due to death or due to lack of efficacy, a composite strategy will be adopted, where participants with the intercurrent event before Week 24 having missing observation(s) after the intercurrent event will have those missing observations(s) imputed by unfavorable values ([Appendix 2](#))
- Population level summary: Mean change from baseline, by AT132 dose level

The estimand framework described above will be applied to all relevant primary and secondary efficacy endpoints.

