4.4.2 Supportive Secondary Endpoints

4.4.2.1 Definition of Endpoints

- Time to reduction in required ventilator support to ≤ 16 hours a day (only in participants who require invasive ventilation) at Week 24
- Change from baseline in Children's Hospital of Philadelphia Infant Test of Neuromuscular Disorders (CHOP INTEND) at Week 24
- Change from baseline in maximal inspiratory pressure (MIP) at Week 24
- Change from baseline in quantitative analysis of myotubularin expression in the muscle biopsy at Week 24
- Change from baseline in quality of life assessments at Week 24 (ie, the Assessment of Caregiver Experience with Neuromuscular Disease [ACEND] and Pediatric Quality of Life Inventory [PedsQL])
- Number (%) of age-appropriate clinically relevant gross motor function milestones attained through Week 24
- Percentage of participants achieving full ventilator independence at Week 24
- Survival

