‡ Duration of sitting in the reference (WHO Multicenter Growth Reference Study) is not clearly defined, so the same age is used for the expected age of achievement for both independent sitting milestones.

The number and percentage of participants achieving each gross motor function milestone will be summarized descriptively by low dose and high dose group by visit week through Week 24. A similar summary will be provided for visits occurring after Week 24.

The denominator of the percentage calculation will only include the participants who attended the visit and are expected to achieve the particular milestone based on their age (i.e., if at the time of an assessment the child is at least the age indicated in [Table 1](#), then they will be considered eligible for the milestone and will be included in the denominator). A child’s eligibility will need to be uniquely determined for each assessment at each time-point.

The denominator values will be included in the table.

The percent of age-eligible milestones that each participant achieves at Week 24 will also be summarized as a continuous (percentage) by visit and via shift table as an ordinal variable, by number and percent of participants in each category (None, at least 1, >1 to half of the expected milestones, >50% to <100% all expected milestones, All expected milestones) at baseline and shift post-baseline.

Number of age-eligible milestones expected at Week 24 (denominator for the calculation for the participant at the visit) is determined based on the age of the participant at the visit and the corresponding number of milestones expected for that age. The numerator of the calculation for the participant at the visit is the number of milestones that they have achieved. The corresponding percentage will be converted to the relevant category. The number of participants falling into each category regardless of age will be summarized at each visit.

Each participant's timeline of achieving the motor milestones will also be presented graphically.

Any assessment done prior to the date of the participant signing Protocol V 5.0 informed consent is assumed to correspond to protocol V1.0 – 4.0 data.

4.4.2.2.7 Percentage of participants achieving full ventilator independence at Week 24

“Full ventilator independence” is defined as: the date of removal from ventilator field on the “Assessment of Ventilator Parameters” eCRF is not blank or “Is subject on a ventilator” = “No” on the same eCRF.

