@Only Applicable to Serum Bile Acid, Total.

Table 11 Analysis Week Window for Weekly Average Hours of Ventilator Support from Diary of Ventilator Dependence

Analysis Week	Analysis Windows (Day)
Baseline	-7 - -1
Week 1	1 - 7
Week 2	8 - 14
Week 3	15 - 21
Week 4	22 - 28
Week 5	29 - 35
Week 6	36 - 42
Week 7	43 - 49
Week 8	50 - 56
Week 9	57 - 63
Week 10	64 - 70
Week 11	71 - 77
Week 12	78 - 84
Week 13	85 - 91
Week 14	92 - 98
Week 15	99 - 105
Week 16	106 - 112
Week 17	113 - 119
Week 18	120 - 126
Week 19	127 - 133
Week 20	134 - 140
Week 21	141 - 147
Week 22	148 - 154
Week 23	155 - 161
Week 24	162 - 168
Week 25	169 - 175
Week 26	176 - 182
Week 27	183 - 189
Week 28	190 - 196
Week 29	197 - 203
Week 30	204 - 210
Week 31	211 - 217
Week 32	218 - 224
Week 33	225 - 231
Week 34	232 - 238
Week 35	239 - 245
Week 36	246 - 252
Week 37	253 - 259
Week 38	260 - 266
Week 39	267 - 273
Week 40	274 - 280
Week 41	281 - 287
Week 42	288 - 294
Week 43	295 - 301
Week 44	302 - 308
Week 45	309 - 315
Week 46	316 - 322
Week 47	323 - 329
Week 48	330 - 336

If more than one observation exists within the analysis window, the observation closest to the scheduled visit day will be selected for that visit. If there are two observations that have the same distance from the scheduled day, the value that is after the scheduled day will be

selected in the analysis. If more than one observation is made on the same day, an average value if continuous or the worst value if categorical will be included in the analysis.

The Follow Up visit will include all data collected beyond 10 days after the last dose of study drug. If there is more than one value, then the value that is closest to day 28 from the last dose of study drug will be selected for the analysis. The same logic will be applied as above for more than one value.

If a table summary for visits is not planned, then visit windowing does not need to be done for that data.

For diary data, results will be mapped to a particular visit week by the following logic, which is the same as in [Table 11](#):

```
avisit="Week "||strip(put(ceil(ady/7),best.))
```

Per protocol, daily diary collection should end after Week 48. However, for some participants it continued longer. For daily diary analysis visits that correspond to a “Month X” official analysis visit name, the avisit calculation above will be converted to the corresponding Month X official analysis according to the analysis windows table.

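### The Week 24 ventilator-independence rule lets a filled removal date outweigh an answer that the child is on a ventilator

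*SAP*

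**What the plan says.** The endpoint, in SAP 1.1.2 and 4.4.2.1, is "Percentage of participants achieving full ventilator independence at Week 24". SAP 4.4.2.2.7 gives the working definition, which uses two fields of the ventilator-parameters form. The first is "the date of removal from ventilator field". The rule then reads "eCRF is not blank or “Is subject on a ventilator” = “No” on the same eCRF". The result is tabulated by dose group at Week 24, and the same parameter is summarised by visit week.

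Four other provisions bear on the rule:

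- **Record selection (SAP 4.10.2).** Table 9, column (a), gives ventilator parameters a Week 24 window of Days 141 to 252. The selection rule is: "If more than one observation exists within the analysis window, the observation closest to the scheduled visit day will be selected for that visit".
- **Intercurrent events (SAP 1.1.3 and Appendix 2).** "For study discontinuation due to death or due to lack of efficacy, a composite strategy will be adopted". After such an event, independence is set to No. Resumed ventilation is not listed as an intercurrent event.
- **Timing (Protocol 5.1.1.11.4).** "Discontinuation of mechanical ventilation can be attempted after the Week 12 visit".
- **Resumption (Protocol 5.1.1.11.2.1).** For children whose support has stopped after the Week 24 visit, the protocol adds: "If ventilator support is resumed, the daily diary completion will resume through Week 48".

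**The concern.** The endpoint's name describes a state at a time point. The date condition describes something else: that a removal was recorded. The two agree only while the child stays off support. Where they disagree, the SAP has no order of precedence, although it sets one for the key secondary endpoint in 4.4.1.1 (milestone form first, Bayley item second).

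At stake is the accuracy of a listed secondary endpoint in very small groups. The primary endpoint (SAP 4.3.1) takes ventilator hours from the daily diary, or from the questionnaire for children dosed under protocol v4 and earlier. One child could therefore contribute more than 0 hours at Week 24 to the primary analysis and be reported as fully independent in the secondary table.

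**Working it through.** The plan gives no figure on this point to reproduce. The check has three parts.

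**1. The rule applied to every combination of the two fields.** SAP rule: date filled OR status = No. Comparison rule: status = No.

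| Removal date | On a ventilator? | SAP rule | Status rule |
|---|---|---|---|
| Filled | Yes | Independent | Not independent |
| Filled | No | Independent | Independent |
| Filled | Missing | Independent | Not confirmed |
| Blank | Yes | Not independent | Not independent |
| Blank | No | Independent | Independent |
| Blank | Missing | Not independent | Not confirmed |

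The SAP rule classes four of the six combinations as independent. In two of those four (date filled with status Yes, and date filled with status missing) the form does not confirm that the child is off the ventilator. The first of these contradicts the form's own answer.

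**2. Whether another provision corrects it.**

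- The closest-record rule chooses which record is used. It does not reconcile two fields on that record.
- The Week 24 window extends 252 − 168 = 84 days past the scheduled day, so a late record and a late removal date can supply the Week 24 result if no closer record exists.
- Appendix 2 covers only study discontinuation due to death or lack of efficacy.
- Discontinuation may be attempted after Week 12 (Day 84), which leaves 168 − 84 = 84 days before Week 24. Removal and resumption could both occur in that interval, but the documents do not report that this happened.
- For visits after Week 24, the protocol expressly provides for resumption, and the by-visit summary uses the same definition.

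**3. Weight of one child.** Formula: 100/n percentage points.

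- Low dose: Protocol 1.4.2 gives 6 children dosed at the July 2020 cutoff. SAP 1.2 gives 3 delayed controls still awaiting dosing, and SAP 1.3 says two controls were never dosed. Assuming no replacement child was dosed, n = 6 + (3 − 2) = 7. Then 100/7 = 14.3 points; with n = 6, 100/6 = 16.7 points.
- High dose: Protocol 1.4.2 gives n = 17, so 100/17 = 5.9 points.
- If no record is discordant, the change is 0.

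**The case against.** The strongest reply is that the conflict may be impossible in the data. The form is not in the documents. If the removal date can be entered only when the child is off the ventilator, or is cleared when support resumes, the 'or' merely rescues records with one blank field. That possibility stands and leaves the frequency unknown. It does not change what the rule says, and neither document states such a constraint.

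A second reply is that the form belongs to a visit and the window rule picks one record, so a date on a Week 16 form need not make a child independent at Week 24. That also stands. A reader might infer that any removal date ever recorded is enough, but the documents do not establish that dates carry forward between forms.

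Two further inferences are tempting and unsupported:

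- The protocol's sentence on resumption might be read as evidence of resumption before Week 24. It concerns children whose support stopped after the Week 24 visit, so it bears on the later rows of the by-visit table.
- The dropped qualifier on acute illness and the perioperative period might be read as a lost safeguard. Its removal is a documented choice, and nothing shows that it protected against resumption. It reads more naturally as an exemption for temporary ventilation.

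Finally, no hypothesis is tested (SAP 2), ventilator data are listed, and hours are plotted by subject (SAP 4.3.2). A discordant child could therefore be found by a careful reader, but the tabulated percentage would remain wrong.

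**Conclusion.** The point holds as a defect in the stated definition. A record with a removal date and an on-ventilator answer is classed as independent, the date is not tied to the visit, and no other provision corrects either feature. The consequence is possible overstatement of a descriptive percentage: about 14 to 17 points per affected child at the low dose and about 6 at the high dose. No error rate is affected.

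The documents do not show that any child has been or will be misclassified; zero is compatible with them. The per-child figures assume the group sizes above and no missing data, since SAP 4.1 bases percentages on participants with non-missing data. Children who left the study before Week 24 through death or lack of efficacy are already set to No and fall outside the point.

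**What to change.** Reword SAP 4.4.2.2.7 as follows:

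- Independence at a visit means that the form answers No to being on a ventilator, on the record chosen by the existing window rule. An answer of Yes overrides any removal date.
- The removal date is used only when the status answer is missing, the date is on or before that visit, and no later ventilator use is recorded up to it.
- The same definition applies to the by-visit summary.
- Records discordant with the hours data are listed. The comparison is with the diary where it was collected, and with the ventilator questionnaire for children dosed under protocol v4 and earlier.

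The questionnaire is needed because a diary check alone would miss most of the low-dose group. The original six were all at least 2 years past dosing on 08 July 2020 (Protocol 1.4.2), so they were dosed by July 2018. Protocol v5 is dated 01 May 2019, and SAP 4.3.1 assigns children dosed before it to the questionnaire.

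The cost is SAP wording and one listing, using fields already collected. The percentage may become slightly less favourable. If there are no discordant records and no dates standing in for a missing status, nothing changes.

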5.1.1.11.5 Assessment of Ventilator Parameters

End tidal CO₂, transcutaneous CO₂, O₂ saturation, and serum bicarbonate (from the local or central laboratory) will provide information about the effectiveness of ventilation.

Assessment of ventilator parameters will include the baseline ventilator settings and changes in ventilator settings over time, end tidal CO₂, transcutaneous CO₂, respiratory rate, O₂ saturation, and serum bicarbonate during clinic visits. During the contact calls, the site will ask the LAR if the subject is currently using ventilator support.

Details on assessment of ventilator parameters will be provided in a separate procedure manual. The above parameters are to be assessed by site personnel during the normal routine site visits through Month 42. As of protocol v12, beginning at the Month 48 visit, the Assessment of Ventilator Parameters will no longer be collected per protocol and decision making related to collection and analysis of clinical ventilator and respiratory parameters will occur by the site and local pulmonologists in collaboration with the Site Investigator.

5.1.1.11.5.1 MIP, MEP, P0.1, and Tidal Volume

Assessment of respiratory strength and endurance will include MIP, MEP, inspiratory occlusion pressure at 0.1 seconds (P0.1), and tidal volume. MIP and MEP will be obtained using a cuffed tracheostomy tube. Details on assessment of respiratory muscle strength and endurance will be provided in a separate procedure manual.

MIP and MEP are noninvasively obtained estimates of respiratory muscle strength. Adult and pediatric reference values exist ([Gaultier, 1983](#); [Wilson, 1984](#)) and this measure is becoming increasingly utilized in the neuromuscular disease setting ([Smith, 2014](#)).

Inspiratory occlusion pressure at 0.1 seconds provides a measurement that represents a weighted sum of the effort of all respiratory muscles active at a given time ([Whitelaw, 1993](#)). This measure is not a separate procedure but rather is a calculated value from data collected during the assessment of MIP.

If a subject has discontinued the use of the ventilator and has 2 assessments with the MIP at 80 cmH₂O, testing for MIP, MEP, and P0.1 will not be required for future visits.

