- ^{bb} Subjects will be administered a course of glucocorticoid therapy commencing Day -1 and continuing for a period of 16 weeks as a preventative measure for immune-mediated hepatic injury. For subjects weighing < 60 kg, the dose will be 1 mg/kg prednisolone orally daily for 8 weeks, then tapered down for 8 weeks per Investigator discretion. For subjects weighing ≥ 60 kg, the dose will be 60 mg prednisolone orally daily for 8 weeks, then tapered down for 8 weeks per Investigator discretion.
- ^{cc} Ursodiol to be dosed at 20 mg/kg/day (divided either BID or TID at the Investigator's discretion) to Week 12 and at the Investigator's discretion thereafter.
- ^{dd} Viral shedding will be assessed on samples of saliva (swab), stool, and urine (diaper collection or urine bag). Collection of each sample type will begin on Day 1 and will continue until each sample type has 3 consecutive data points at or below the limit of detection (BLOD). Sponsor will notify site when collection can cease. Not conducted at Week 10 or 14.
- ^{ee} Subjects in Germany will not have a wrist X-ray. After the Week 48 visit, wrist X-ray only needs to be performed annually thereafter (Month 24, Month 36). As of protocol v12, the wrist X-ray assessment will no longer be collected at Month 48 visit onward.
- ^{ff} As of protocol v12, these assessments will no longer be collected at Month 48 visit onward.

5.6 Schedule of Events for Subjects Treated with AT132: Month 72 (Year 6) – Month 120 (Year 10) (End of Study)

Study Phase/Visit	Month 72	Month 84	Month 96	Month 108	Month 120
Study Day	2190	2555	2920	3285	3650
Visit Window (days)	±60	±60	±60	±60	±60
Physical Examination ^a	X	X	X	X	X
Ventilator Dependence Questionnaire ^b	X	X	X	X	X
Samples for:	X	X	X	X	X
Safety labs (hematology) (central lab) ^{c,d}	X	X	X	X	X
Safety labs (chemistry) (central lab) ^{d,e,f,g} Comprehensive metabolic profile ALT, AST, Total and direct bilirubin, GGT Serum bile acids, total (fasting preferred) PTT and PT/INR Troponin I and T CK Alpha fetoprotein	X	X	X	X	X
Liver ultrasound (local) ^f	X	X	X	X	X
Motor milestone assessments ^h	X	X	X	X	X
ACEND	X	X	X	X	X
Clinical global impression scales ⁱ	X	X	X	X	X
Swallowing questionnaire	X	X	X	X	X
Secretions management assessment ^j	X	X	X	X	X
AEs/concomitant medications	X	X	X	X	X

NOTE: Long-term follow-up visits and/or assessments after the 5-year (Month 60) visit can be done remotely per discretion of investigator in consultation with Medical Monitor.

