Appendix 4: Assessment of Time Off of Ventilator

Site No.	Subject ID	Date of Assessment (DD/Mon/YYYY):
Subject No: 1 ____ - 9 ____		____/____/20 ____
Ventilator Dependence Questionnaire		

**1. Over the past 24 hours,
what type of ventilation
has your child used?**

- BiPAP/CPAP
- Invasive
- None (do not complete question 2)

**2. Over the past 24 hours,
total number of minutes
or hours the child has
spent off of ventilator
support?**

____ # of hours

OR

____ # of minutes

Name of parent/LAR/caregiver providing information: _____

Date of completion: _____

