3.0	10-Jan-2024	Baseline Definition (4.10.1)	Baseline definition updated to exclude information from INCEPTUS study.	Aligning SAP to protocol Amendment version 11.0
3.0	10-Jan-2024	Analysis Windows	Analysis windows have been updated to accommodate the longer follow-up to align to Protocol V 11.0. Additional details on windowing daily diary data have been added	Aligning SAP to protocol Amendment version 11.0; adding details for clarity of definitions
4.0	15-Apr-2024	Protocol Deviations (4.2.2)	Category definition for the protocol deviations has been updated.	Aligning SAP to Protocol Deviation Plan
4.0	15-Apr-2024	Percentage of participants achieving full ventilator independence at Week 24 (4.4.2.2.7)	The following statement has been removed: "Note: this endpoint definition is different from what is specified in the protocol at the time of SAP development (V11.0). It was updated from "Percentage of participants achieving full ventilator independence in the absence of acute illness and perioperatively at Week 24" to "Percentage of participants achieving full ventilator independence at Week 24" in the SAP".	Aligning SAP to protocol Amendment version 12.0

SAP Version	Approval Date	SAP Section(s)	Change	Rationale
4.0	15-Apr-2024	Table 6. Potentially Clinically Significant Criteria for Vital Signs (4.6.2.3) Table 7. Potentially Clinically Significant Criteria for ECG (4.6.2.4)	For Age Group, "> 7 years" has updated to "≥ 8 years".	For clarification purpose.
4.0	15-Apr-2024	Hospitalization (4.6.2.5.3)	Category definition for the annualized hospitalization rate has been updated.	Correcting a typographical error
4.0	15-Apr-2024	Analysis Windows (4.10.2)	Analysis windows have been updated according to schedule of assessment in Protocol V 11.0. Additional details have been added for analysis week windows for weekly average hours of ventilator support from diary of ventilator dependence.	Aligning SAP to schedule of assessments in protocol; analysis visit windows should have varied across endpoints based on protocol-defined visit schedule
4.0	15-Apr-2024	Appendix 2 Unfavorable Values for Efficacy Estimand Imputation (5.2)	An item of "Reduction in require ventilator support to ≤ 16 hours/day" has been removed.	Not needed to apply the imputation rule for this variable

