The number and percentage of participants achieving full ventilator independence at Week 24 will be summarized descriptively by low dose and high dose groups.

In addition, a summary by visit week of the same parameter will be provided by dose level.

All ventilator parameter data will be listed.

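### The by-visit ventilator independence table uses only a form that protocol v12 drops from Month 48, so its Month 54 and Month 60 rows lose mainly high-dose children

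*SAP*

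**What the plan says.** SAP 4.4.2.2.7 counts a child as fully ventilator independent if "the date of removal from ventilator field on the “Assessment of Ventilator Parameters” eCRF is not blank", or if the same form records that the child is not on a ventilator. No second source is named. After the Week 24 result by dose, the section adds "In addition, a summary by visit week of the same parameter will be provided by dose level", with no last visit stated.

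Protocol 5.1.1.11.5 says: "As of protocol v12, beginning at the Month 48 visit, the Assessment of Ventilator Parameters will no longer be collected per protocol". The schedule in Protocol 5.5 agrees. It marks the assessment through Month 42 and leaves Months 48, 54 and 60 empty, and footnote ff reads "As of protocol v12, these assessments will no longer be collected at Month 48 visit onward".

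SAP Table 9 column (a), which covers ventilator parameters, still has windows for Month 48 (Days 1370-1551), Month 54 (1552-1734) and Month 60 (1735 onward), and none after that. The SAP version history explains why: "Analysis windows have been updated according to schedule of assessment in Protocol V 11.0". SAP version 4.0 is dated 15 April 2024, a month before protocol v12.

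The Ventilator Dependence Questionnaire does continue. Under Protocol 5.1.1.11.2.2 caregivers "complete the ventilator dependence questionnaire at clinic and contact visits through Month 120". Its first item (Appendix 4) asks the type of ventilation over the past 24 hours: BiPAP/CPAP, Invasive or None. Table 9 column (i) windows it to Month 120, and SAP 4.3.1 already converts None to zero hours for the primary endpoint.

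**The concern.** The independence table has one source, and that source stops partway through the visits for which the table has windows. The stop is by calendar date, and dose is tied to calendar date: most low-dose children were treated first, and Part 2 high-dose children later. Loss of late records therefore depends on dose.

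SAP 4.1 bases percentages on participants with non-missing data, so children without the form leave the denominator. Case mix shifts too. Part 2 required invasive support for 20 to 24 hours a day at entry, while Part 1 accepted any mechanical support, so a high-dose row without its Part 2 children describes a different group. SAP 1.3 says the remaining purpose is to describe the low-dose and high-dose groups, which is exactly the contrast that these rows would distort. The direction of any distortion cannot be worked out from the documents.

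**Working it through.** The plan gives no figure to reproduce here, so the check is date arithmetic plus head counts.

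**Rule.** Visit date = dosing date + (study day - 1). Study days come from Protocol 5.5: Month 48 = 1460, Month 54 = 1643, Month 60 = 1825. The cut-off is the v12 date, 17 May 2024, taken as effective at every site.

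**Dosing date after which a visit falls after v12**
- Month 48: 17 May 2024 - 1459 days = 19 May 2020
- Month 54: 17 May 2024 - 1642 days = 18 November 2019
- Month 60: 17 May 2024 - 1824 days = 20 May 2019

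**First six low-dose children.** Protocol 1.4.2 says all were at least 2 years from dosing at the 8 July 2020 data cut-off, so they were dosed by about 8 July 2018. They reached Month 48 by 6 July 2022, Month 54 by 5 January 2023 and Month 60 by 6 July 2023. None of these visits is lost to v12.

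**High-dose children overall.** Protocol 1.4.2 reports 17 at that cut-off, so all were dosed by 8 July 2020. Their latest possible visits are 6 July 2024 (Month 48), 5 January 2025 (Month 54) and 6 July 2025 (Month 60). Month 48 can be lost only by a child dosed between about 19 May and 8 July 2020, which may be nobody.

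**Part 2 children.** Protocol 7.4.2.1 places all Part 2 dosing under v5 (1 May 2019) or later. Month 60 therefore falls no earlier than 1 May 2019 + 1824 days = 28 April 2024. Only a child dosed between 1 and about 20 May 2019 would reach Month 60 before v12.

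**Early high-dose children in Part 1.** Protocol 1.4.2 describes Week 24 biopsy results in Cohort 2 as available when v5 was written. Those children were dosed by about 1 May 2019 - 167 days = 15 November 2018 and reached Month 60 by about 13 November 2023. They keep the row.

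**Head counts**
- 17 high dose + 6 low dose + 3 controls not yet dosed at v8/v9 = 26, which equals the planned 16 + 10.
- SAP 1.3 excludes two controls who were never dosed, so one was dosed later at the low dose: 26 - 2 = 24 treated, 17 high and 7 low.
- If Part 2 enrolled its planned 10 and the 3 undosed controls were all in Part 2, then 10 - 3 = 7 Part 2 children received the high dose.
- Three high-dose children had died by the July 2020 cut-off. If none was in Part 2, 7 lose Month 60; if all were, 7 - 3 = 4. Part 1 controls treated after v5 would add to this.
- Against 17 - 3 = 14 surviving high-dose children, the loss is 4/14 = 29% to 7/14 = 50%, before other withdrawals.
- The seventh low-dose child, dosed under v9 (15 January 2021) or later, reaches Month 48 no earlier than 15 January 2021 + 1459 days = 13 January 2025. At most one low-dose child is affected.

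**The case against.** The strongest reply is that long-term ventilation is reported anyway. SAP 4.3.2 summarises hours of support by visit and dose and plots them by subject, None counts as zero hours, and column (i) runs to Month 120. This helps only in part. SAP 4.3.1 assigns the questionnaire to children without a baseline diary. Children dosed under v5 or later, including all of Part 2, are assigned the diary, which under the protocol ends by Week 48. Read literally, the hours table does not clearly cover the children who drop out of the independence table. A programmer might fill the gap from column (i), but the SAP does not say to.

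A second reply is that late rows were never clearly promised: the endpoint is at Week 24 and the sentence speaks of visit weeks. That reading is possible, but column (a) carries windows to Month 60.

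A third is that a removal date recorded before Month 48 could be carried forward. The SAP has no such rule, and Protocol 5.1.1.11.2.1 allows for ventilation being resumed, which carry-forward would miss.

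Three points against the concern stand. The output is descriptive, with no hypothesis test. Dosing dates and site adoption of v12 are inferred. The questionnaire is a caregiver's report of the past 24 hours, so it is a close proxy for the eCRF item and not the same measurement.

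A reader might also infer that ten years of durability data are lost, or that the late high-dose rows vanish. The documents do not support either. Column (a) has no rows for Months 72 to 120 in either dose group, so that is an equal coverage gap, and the questionnaire data are still collected. High-dose rows shrink but do not empty, because early Cohort 2 children passed Month 60 before v12.

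**Conclusion.** The concern holds for the Month 54 and, above all, the Month 60 rows of the by-visit independence summary. Followed as written, Month 60 loses roughly 4 to 7 high-dose children and at most one low-dose child, so the dose columns there should not be compared. Month 54 loses those dosed after about 18 November 2019, a number that cannot be fixed from the documents. Month 48 may lose few or none.

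The size rests on four assumptions: v12 took effect on its date at every site, Part 2 enrolled 10, the three undosed controls were all Part 2, and no other child withdrew. Later adoption of v12 would reduce the loss but not reverse its direction. The Week 24 secondary endpoint is not touched. This is a defect in a supplementary descriptive table, but it is dose-related and can be repaired with data already collected, so it should be corrected before the final database lock.

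**What to change.** Add to SAP 4.4.2.2.7 a rule limited to visits from Month 48 onward at which the ventilator-parameters eCRF was not collected:
- independence is Yes if the questionnaire's ventilation type is None;
- No if it is Invasive or BiPAP/CPAP;
- missing if there is no questionnaire.

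Window these records by Table 9 column (i), optionally through Month 120, and flag the source in the table so that the change at Month 48 is visible. Show the number contributing in each dose group at each visit.

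Two limits matter. An absent questionnaire must not be scored as ventilator dependence. The rule must not reach back to Week 24, where Protocol 5.5 does not schedule the questionnaire; that endpoint stays on the eCRF.

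If the sponsor does not want a mixed source, the alternative is to state that the by-visit independence summary ends at Month 42.

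Either choice costs a few lines of SAP text, and the first also needs modest programming. No new data are required. The price of the first is reliance on a 24-hour caregiver report, which the flag discloses.
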